#### 4 STUDY SYNOPSIS

Name of Sponsor/Company: Sun Pharma Global FZE	Individual Study Table Referring to Part of the Dossier:	(For National Authority Use Only)		
Name of Product: Tildrakizumab				
Name of Active Ingredient: Tildrakizumab	Volume:			
Title of Study: A Long-Term Extension Study to Demonstrate Safety of Tildrakizumab in Subjects with Psoriatic Arthritis who Have Previously Completed Study with Tildrakizumab				
Study Sites: It is planned that at least 70 sites will be initiated for this study in at least 8 countries. All study sites used in the parent study can enter subjects to this long-term extension study, based on subject eligibility.				
Publication(s): None.				
Planned Study Period: Approximately June 2018 to an anticipated date of approximately 4 years after last subject entered from contributing parent study.	Development Phase: Phase 2b/3			
Objectives: Primary Safety Objectives To assess the long-term safety of tildrakizumab given to psoriatic arthritis (PsA) subjects by evaluation of: 

Incidence and intensity of all adverse events (AEs),

Changes in vital signs, laboratory assessments, electrocardiograms (ECGs), and Columbia-Suicide Severity Rating Scale (C-SSRS),

Immunogenicity of multiple-dose administration of tildrakizumab in these subjects.

				
Methodology: This is a long-term extension study of tildrakizumab in subjects with PsA who have previously completed the treatment period of study with tildrakizumab. The eligible subjects will continue to be administered one of the following dose regimens – 200 mg Q4W, 200 mg Q12W or 100 mg Q12W to maintain the blind of the ongoing parent study to at least Week 52. Thereafter, all subjects begin migrating to receive 100 mg tildrakizumab SC injection Q12 weeks in an open-label fashion for up to an additional 4 years in this long-term extension study, provided that they meet clinical response criteria. No randomization will occur for this long-term extension study. Treatment allocation will be based upon the dose regimen assigned at the end of the treatment period in the parent study with all subjects receiving tildrakizumab. With this amendment, all subjects shall receive 100 mg tildrakizumab, every (Q) 12 weeks in the long-term extension study. All subjects who meet the inclusion criteria and complete the parent study treatment (up to Week 48 for the parent Phase 2 study, with return for the End of Treatment [EoT] visit at Week 52), and who meet defined clinical response criteria will receive 100 mg tildrakizumab, Q12 weeks for up to an additional 4 years. Subjects who completed the treatment period of their parent study and entered the parent study wash-out phase prior to study site activation of the long-term extension protocol will also be eligible for inclusion in the long-term study (when available) provided all eligibility criteria are met.				

Name of Sponsor/Company: Sun Pharma Global FZE	Individual Study Table Referring to Part of the Dossier:	(For National Authority Use Only)
Name of Product: Tildrakizumab		
Name of Active Ingredient: Tildrakizumab	Volume:	
	Page:	

The study will consist of a Baseline visit (Week 0) which will be the same as Week 52 of the parent study 12-weekly visits (from Week 8) up to approximately 2 years from the start of the extension study, followed by 24-weekly visits thereafter (from Week 104) up until approximately 4 years after the start of the study (approximately 5 years from the start of the parent study).
 
The parent Phase 2 study will retain a blind status at the time of the initiation of the extension study (double-blind for the PsA study, i.e., only the Sponsor and designated contract research organization [CRO] team members not directly related to the clinical conduct of the study will have been unblinded). Safety assessments will be conducted at the 12 weekly or 24-weekly visits in accordance with the Schedule of Assessments.
 
All scheduled visits will occur at the study site. However, should unusual circumstances such as public health emergency (i.e. pandemic with an infectious agent) or natural disasters arise, video conference or teleconference between the subject and site investigator will be permitted as deemed appropriate by the Sponsor provided no physical examination is needed for the visit. In this unusual circumstance, self-injection made by the subject at subject's home is allowed in order to guarantee treatment continuity.
 
When all subjects have completed the PsA parent Phase 2 study, the blind will no longer need to be maintained for the cohort, and this long-term extension study will have the option to become open-label for those subjects. Note: the timing of switch to an open-label design may differ across the cohorts of subjects entered, depending on the parent study. If other studies are also included in the long-term extension study, similar considerations for maintenance of blind will be necessary. Those subjects will be entered as separate cohorts and procedures such as continued double-dummy dosing regimens will be utilized, even after other parent Phase 2 cohorts have the option to switch to open-label.
 
Subjects not deriving sufficient clinical benefit in the opinion of the Investigator at any time after the initiation of this long-term extension study should be discontinued from investigational medicinal product (IMP), and receive clinical care as determined by the Investigator.
 
With the exception of those who withdraw informed consent, subjects who withdraw from IMP during the long-term extension study will undergo the EoT assessments approximately 4 weeks after their last administration of IMP. Subjects who complete treatment to Week 200 will return for a Follow-up assessment at Week 208 (4 years).
 
No independent assessor is needed to assess efficacy measurements. There will be no efficacy assessments during the LTE study. The Principal Investigator (PI)/designee will be responsible for performing safety evaluations.
 
Clinical Adjudication Committee will be established to evaluate cardiovascular events.
 
End of study is defined as the last visit of the 4-year treatment period (Week 208, EoT/Follow-up) for the last global subject.
		

Name of Sponsor/Company: Sun Pharma Global FZE	Individual Study Table Referring to Part of the Dossier:	(For National Authority Use Only)
Name of Product: Tildrakizumab	Volume:	
Name of Active Ingredient: Tildrakizumab	Page:	

1 Subjects from parent Phase 2 study who do not meet inclusion/exclusion criteria at Wk 52 of parent study (using laboratory data from Wk 48 for efficacy response criteria), or who in the opinion of the Investigator would not benefit from continued treatment with Tildrakizumab, will enter the 20-Wk wash-out phase in accordance with the parent protocol (Not shown). All eligible subjects will continue to long-term extension study, commencing at Wk 52 of parent study (B/L) and receive tildrakizumab 100 mg q12 wks (Week 0 of long-term extension study). Subjects who completed the treatment period of their parent study and entered the wash-out phase prior to study site activation of the long-term extension protocol will also be eligible for inclusion in the long-term study (when available) provided they meet eligibility criteria.

2 B/L = Wk 0 of the long-term extension study, and will be the same as Wk 52 of the parent study.

3 The long-term extension study will remain double-blind for all subjects from the parent Phase 2 PsA study until such point that the PsA study is complete with database locked. At that time, the long-term study will have the option to become open-label for subjects entering from Phase 2 parent study. Note the timing of the switch to open-label may differ across the cohorts of subjects, dependent on the parent study. The IMP administration will continue Q12 weeks, while the safety assessments will be Q12 weeks in the first two years, followed by Q24 weeks in the last 2 years.

Name of Sponsor/Company: Sun Pharma Global FZE	Individual Study Table Referring to Part of the Dossier:	(For National Authority Use Only)
Name of Product: Tildrakizumab		
Name of Active Ingredient: Tildrakizumab	Volume:	
Page:		

Number of Subjects: Up to 286 subjects with PsA could be enrolled from the parent Phase 2 study.
		

Diagnosis and Main Criteria for Inclusion:
 
Inclusion Criteria:
 
Subjects may be included in the study if they meet all of the following criteria:
 
 
1. Subject has provided written informed consent for this long-term extension study.
 
2. Subjects with PsA who met the inclusion criteria of the parent study and completed the parent study treatment period (e.g., up to Week 48 for the parent Phase 2 study, with return for the EoT assessment at Week 52).
 
3. PsA subjects who achieved a 20% reduction from Baseline in American College of Rheumatology (ACR)20 response criteria at Week 52, AND the subject has received sufficient clinical benefit, in the opinion of the Investigator, to support continued treatment with tildrakizumab.
 
 
This criterion using response criteria at Week 52 will apply to all subjects, including those subjects who enter the study from the wash-out phase of their parent study (after Week 52) due to the timing of study site activation of the long-term extension study.
 
 
4. No concomitant use of both leflunomide and methotrexate simultaneously.
 
5. No history of active tuberculosis (TB) or symptoms of TB.
 
 
Exclusion Criteria:
 
Subjects should be excluded from the study if they meet any of the following criteria:
 
 
1. New onset during the parent study of arthritic conditions other than the subject's original condition.
 
2. Female subjects of childbearing potential who do not agree to abstain from heterosexual activity or practice a dual method of contraception, for example, a combination of the following: (1) oral contraceptive, depo-progesterone, or intrauterine device; and (2) a barrier method (condom or diaphragm). Male subjects with female partners of childbearing potential who are not using birth control as described above must use a barrier method of contraception (e.g., condom) if not surgically sterile (i.e., vasectomy). Contraceptive methods must be practiced upon entering the study and through 16 weeks after the last dose of IMP. If a subject discontinues prematurely, the contraceptive method must be practiced for 16 weeks following final administration of IMP.
 
3. Female is pregnant or breastfeeding, or planning to become pregnant or initiate breastfeeding while enrolled in the study or up to 16 weeks after the last dose of IMP.
 
4. Subject has previously been enrolled in this long-term extension study.
 
5. Any condition that in the opinion of the Investigator represents an obstacle for study conduct and/or represents a potential unacceptable risk for the subject.
 
6. Subject has an active infection or history of infections as follows: 
 
– a serious infection, defined as requiring hospitalization or intravenous anti-infectives within 8 weeks prior to the first IMP dose of the extension study, with the last dose having been received within 7 days of start of the extension study,
 
– recurrent or chronic infections, e.g., chronic pyelonephritis, chronic osteomyelitis, bronchiectasis, or other active infection that, in the opinion of the Investigator, might cause this extension study to be detrimental to the subject.
 
 
 
		

Name of Sponsor/Company: Sun Pharma Global FZE	Individual Study Table Referring to Part of the Dossier:	(For National Authority Use Only)
Name of Product: Tildrakizumab		
Name of Active Ingredient: Tildrakizumab	Volume:	
Page:		

7. Major chronic inflammatory or connective tissue disease other than PsA (e.g., rheumatoid arthritis, systemic lupus erythematosus, Lyme disease, gout, Crohn's disease, etc).
 
8. Known diagnosis of fibromyalgia, regional pain syndromes or active uveitis/symptomatic inflammatory bowel disease requiring therapy.
 
9. Subject has any concurrent medical condition or uncontrolled, clinically significant systemic disease (e.g., renal failure, heart failure, hypertension, liver disease, diabetes, or anemia) that, in the opinion of the Investigator, could cause continued treatment to be detrimental to the subject.
 
10. Subject has a known history of infection with hepatitis B, hepatitis C, or human immunodeficiency virus during the parent study.
 
11. Subject had myocardial infarction, unstable angina pectoris, or ischemic stroke within the past 6 months prior to the first IMP dose for this extension study.
 
12. Subject has any active malignancy, including evidence of cutaneous basal or squamous cell carcinoma or melanoma.
 
13. Subject has a history of malignancy EXCEPT treated and considered cured cutaneous basal or squamous cell carcinoma, in situ cervical carcinoma, OR in situ breast ductal carcinoma.
 
14. Subjects with a history of alcohol or drug abuse during the parent study.
 
15. Significant risk of suicidality at the Baseline assessment of this extension study based on the Investigator's judgment or, if appropriate, as indicated by a response of "yes" since the last visit to question 4 or 5 in the suicidal section, or any response in the behavioral section of the C-SSRS.
 
16. Subject has a need for use of a live vaccine within 10 weeks of final anticipated dose of IMP for the long-term extension study.
 
17. Concomitant use of prohibited medications or use of commercially available or investigational biologic therapies (other than tildrakizumab) for psoriasis or PsA.
 
General
 
18. Subjects who have been placed in an institution on official or judicial orders.
 
19. Subjects who are related to or dependent on the Investigator, Sponsor, or study site such that a conflict of interest may arise.
		

Test Product, Dose and Mode of Administration:
 
The IMP will be supplied as a [REDACTED] and administered subcutaneously (SC). All subjects will be dosed at the same time points with 100 mg tildrakizumab Q12 weeks (one 1-mL injection of 100 mg/mL) at Weeks 0, 8, 20, 32, 44, 56, etc and all subsequent 12-weekly time points to Week 200.
		

Reference Therapy, Dose and Duration of Administration:
 
There will be no placebo comparator in this study.
 
Investigational [REDACTED] and administered SC. Self-administration made by the subject at the subject's home is contemplated only if unusual circumstances, such as public health emergency (i.e. pandemic with an infectious agent) or natural disasters, arise.
		

Duration of Treatment:
 
Up to 200 weeks of continued tildrakizumab treatment from the parent study, followed by an EoT/Follow-up assessment at Week 208 (4 years), or approximately 4 weeks after last dose of IMP for those withdrawing early.
		

Name of Sponsor/Company: Sun Pharma Global FZE	Individual Study Table Referring to Part of the Dossier:	(For National Authority Use Only)
Name of Product: Tildrakizumab	Volume:	
Name of Active Ingredient: Tildrakizumab	Page:	

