**Table 9-1 Schedule of Assessments for PsA Subjects**

Visit a	1	2	3	4	5	6	7	8	9	10	11	12	13	14	15	16	17	18	19	EoT/ FU
Week (± 7D)	0 b	8	20	32	44	56	68	80	92	104	116	128	140	152	164	176	188	200	208 c	
Written informed consent	X																			
Inclusion/Exclusion criteria	X																			
Demographic information d	X																			
Physical examination	X					X				X					X			X	X	
Vital signs	X	X	X	X	X	X	X	X	X		X		X		X	X		X	X	
AEs/Concomitant medications e	X	X	X	X	X	X	X	X	X	X	X	X	X	X	X	X	X	X	X	
Medical/Medication history e	X																			
ECG	X					X				X					X				X	
IMP administration f	X	X	X	X	X	X	X	X	X	X	X	X	X	X	X	X	X	X		
Hematology/chemistry/urinalysis g	X		X			X				X					X			X	X	
Lipids h	X		X			X				X					X			X	X	
Urine pregnancy test i	X	X	X	X	X	X	X	X	X	X		X		X		X		X	X	
hsCRP and ESR i	X		X			X				X				X				X	X	
Anti-drug antibodies	X		X			X				X				X				X	X j	
PK sample h	X		X			X				X				X				X	X	
C-SSRS k	X	X	X	X	X	X	X	X	X	X	X	X	X	X	X	X	X	X	X	

Abbreviations: AE = adverse event; BL = Baseline; C-SSRS = Columbia-Suicide Severity Rating Scale; D = days; ECG = electrocardiogram; ESR = erythrocyte sedimentation rate; EoT = End of Treatment; FU = Follow-up; hsCRP = high sensitivity C-reactive protein; IMP = investigational medicinal product; M = months; PK = pharmacokinetic; PsA = psoriatic arthritis; W = weeks; Y = year(s).

- a Visits will be scheduled every 12 weeks in the first two years, followed by every 24 weeks in the last two years. Collection of AEs and concomitant medications, as well as any unscheduled safety assessment deemed appropriate in the opinion of the Investigator to ensure subject safety, will be performed at each visit. In addition, following completion and database lock of the parent PsA Phase 2 study, the long-term extension study will have the option to become open-label for these subjects.
- b The BL visit of the study Visit 1 (Week 0, Day 1) will be the same as Visit 16, Week 52 of parent PsA study (or later for subjects who entered the wash-out phase from the parent study due to the timing of study site activation of the long-term extension study).
- c Subjects who withdraw from IMP at any time will complete the EoT/FU assessments approximately 4 weeks after administration of the last dose of IMP.

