#### **9.1.3.1.2 Treatment Period (Week 0 through Week 200)**

During the 4-year long-term extension treatment period, subjects will receive 100 mg tildrakizumab, SC, Q12 weeks dosing regimen as described in [Section 9.1](#). The assessments and procedures listed in [Table 9-1](#) will be performed at 12-weekly intervals to Week 104 then 24-weekly intervals to Week 200 and include:

- Record physical examination findings (annually at Weeks 56, 104, 152, and 200 only).
- Perform a urine pregnancy test by urine dip stick (at the site using materials supplied by the central laboratory).
- Perform safety assessments including:
  - perform a 12-lead ECG (annually at Weeks 56, 104, 152, and 200 only),
  - vital signs (all visits except Week 116, 140, 164, and 188),
  - C-SSRS (all visits except Week 140, 164, and 188),
  - routine safety laboratory assessments (hematology, chemistry, and urinalysis, Weeks 20, 56, 104, 152, and 200 only). Blood samples are to be collected (pre-dose) after ECG and vital sign measurements,
  - lipids (Weeks 20, 56, 104, 152, and 200 only),
  - hsCRP and ESR measures at Week 8, 20, 56, 104, 152, and 200 only, to be used for determination of potent AEs should they rise unexpectedly (ESR will be performed at the site using materials supplied by the central laboratory. hsCRP samples will be sent to the central lab and analyzed by central lab),
  - AEs (all visits),
  - record concomitant medications(all visits),
- Obtain a PK sample (Weeks 20, 56, 104, 152, and 200 only).
- Obtain a blood sample for ADA assessments (Weeks 20, 56, 104, 152, and 200 only).
- Administer IMP (Weeks 0, 8, 20, 32, 44, 56, 68, 80, 92, 104, 116, 128, 140, 152, 164, 176, 188, and 200).

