### 11.3.1 Clinical Laboratory Tests

Unless otherwise indicated, all chemistry and hematology parameters will be analyzed using a central laboratory. The following parameters will be collected:

Laboratory Testing Profile	Tests Included
Blood Chemistry	Sodium, potassium, chloride, bicarbonate/CO 2 , blood urea nitrogen, serum creatinine, fasting glucose, albumin, alkaline phosphatase, AST, ALT, total bilirubin, direct bilirubin, indirect bilirubin, total protein, calcium, gamma-glutamyl transferase, creatine kinase
Hematology	Hemoglobin, hematocrit, WBC with differentials (monocytes, eosinophils, basophils, neutrophils, lymphocytes) as an absolute value, RBC count, platelet count, ESR a
Urinalysis	Specific gravity, pH, semi-quantitative “dipstick” evaluation of glucose, protein, bilirubin, ketones, leukocytes, blood  Microscopy and/or culture to be performed if clinically indicated or if urinalysis results positive (blood, protein or leukocyte esterase/WBC).  Urine hCG pregnancy testing for women of childbearing potential a ; may be repeated more frequently than indicated if required by local practice, if a menstrual cycle is missed, or if potential pregnancy is suspected.

Lipid Panel	Total cholesterol, low density lipoprotein, high density lipoprotein, triglycerides, apolipoprotein A-1, B
Acute-phase Reactants	hsCRP

Abbreviations: ALT = alanine aminotransferase; AST = aspartate aminotransferase; CO2 = carbon dioxide; ESR = erythrocyte sedimentation rate; hCG = human chorionic gonadotropin; hsCRP = high sensitivity C-reactive protein; RBC = red blood cells; WBC = white blood cells.

a Urine pregnancy tests and ESR will be performed at the study site using materials supplied by the central laboratory.

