### **11.3.2 Pregnancy Testing**

For female subjects of childbearing potential, a serum pregnancy test will be performed at the Screening visit of the parent study only. Urine pregnancy test with sensitivity of at least 25 mIU/mL, will be performed according to the Schedule of Assessments ([Table 9-1](#)). If at any point during the study there is a case of a positive urine human chorionic gonadotropin test, the subject will have IMP stopped and will be withdrawn from the study.

Pregnancy tests will also be performed whenever 1 menstrual cycle is missed during the treatment period (or when potential pregnancy is otherwise suspected), to confirm the subject has not become pregnant during the study. Pregnancy tests may also be repeated as per request of IECs/ IRBs or if required by local regulations.

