The parent Phase 2 study will retain a blind status at the time of the initiation of the extension study. One randomized dose group in the PsA study will be receiving tildrakizumab 200 mg q4 weeks at the end of the parent Phase 2 study. In order to allow continued q4 week dosing in the extension study, and to maintain the blinding status of the parent Phase 2 study (which will remain ongoing at initiation of first subject entered into the extension study), all subjects entered to this extension study will additionally attend interim visits q4 weeks for IMP administration (tildrakizumab 200 mg or dummy placebo). The interim dosing visits will also be used to record AEs and concomitant medications and any other evaluations as deemed necessary by the Investigator to ensure subject safety.

All scheduled visits will occur at the study site. However, should unusual circumstances such as public health emergency (i.e. pandemic with an infectious agent) or natural disasters arise, video conference or teleconference between the subject and site investigator will be permitted as deemed appropriate by the Sponsor provided no physical examination is needed for the visit. In this unusual circumstance, self-injection of study medication made by the subject at home is acceptable.

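### The emergency remote-visit rule allows home self-injection at visits where a urine pregnancy test is due, and no off-site method for the test is given

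*Protocol*

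**What the plan says.** The remote-visit rule is in the protocol synopsis (Methodology), protocol 9.1.1 and SAP 3.1. In a public health emergency or natural disaster, a video or telephone visit "will be permitted as deemed appropriate by the Sponsor provided no physical examination is needed for the visit". The synopsis adds that "self-injection made by the subject at subject's home is allowed in order to guarantee treatment continuity", and SAP 3.1 that "self-injection of study medication made by the subject at home is acceptable". In 9.1.1 the self-injection sentence breaks off, so the synopsis and the SAP are the texts to rely on.

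On where the urine pregnancy test is done:

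- Protocol 9.1.3.1.1, 9.1.3.1.2 and 9.1.3.1.3 (baseline, treatment period, end of treatment) all place the dip stick at the site.
- The footnote to the table in 11.3.1 says: "Urine pregnancy tests and ESR will be performed at the study site using materials supplied by the central laboratory".
- Table 9-1 footnote i specifies a dip stick but no location, and 11.3.2 gives no location either.

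Under 11.3.2, after a positive urine test, "the subject will have IMP stopped and will be withdrawn from the study".

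The other home-dosing text, in 10.2.3 (Storage), concerns a study nurse giving IMP at home. It covers storage and transport of IMP and does not mention pregnancy testing.

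**The concern.** The rule protects continuity of dosing, and physical examination is the only scheduled assessment that it names as a bar to a remote visit. The pregnancy test decides whether dosing may continue, yet it is not a condition of the home dose and has no described off-site form. A site and subject following the remote-visit paragraph could therefore complete a visit and a home injection with the scheduled test not done.

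What is at stake is continued dosing in an undetected pregnancy, which the protocol sets out to prevent: pregnancy is an exclusion (9.3.2) and a mandatory reason to stop IMP (9.3.5). Endpoints, analyses and error rates are not affected.

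**Working it through.** The plan gives no figure to reproduce. The check cross-tabulates the visit schedule.

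**Inputs**

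- Dosing visits (9.1.3.1.2): Weeks 0, 8, 20, 32, 44, 56, 68, 80, 92, 104, 116, 128, 140, 152, 164, 176, 188, 200. Total 18.
- Physical examination at dosing visits: Week 0 (9.1.3.1.1) and Weeks 56, 104, 152, 200 (9.1.3.1.2). Total 5.
- Urine pregnancy test at dosing visits (Table 9-1): Weeks 0, 8, 20, 32, 44, 56, 68, 80, 92, 104, 128, 152, 176, 200. Total 14.

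**Step 1: dosing visits that can be remote.** 18 − 5 = 13: Weeks 8, 20, 32, 44, 68, 80, 92, 116, 128, 140, 164, 176, 188.

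**Step 2: of these, visits with a test due.** Table 9-1 has no test at Weeks 116, 140, 164 and 188. So 13 − 4 = 9: Weeks 8, 20, 32, 44, 68, 80, 92, 128, 176.

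**Step 3: other readings of the schedule.**

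- In the available copy, the examination row of Table 9-1 falls at Week 164 rather than Week 152. Taken literally, Week 152 joins the list and the count is 10.
- In the SAP's amended schedule (Table 1), again as its columns read, a test is marked at all 18 dosing visits. With the examination weeks of 9.1.3.1.2, all 13 visits from Step 1 have a test due.
- Columns may have shifted in either table. No reading gives fewer than 9.

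**Step 4: effect of one missed test.** This assumes no catch-up or unscheduled test in between.

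| Schedule | Missed test | Interval as planned | Interval without it | Doses strictly between tests |
|---|---|---|---|---|
| Table 9-1, years 3–4 | Week 128 | 128 − 104 = 24 weeks | 152 − 104 = 48 weeks | 1 (Week 116) becomes 3 (116, 128, 140) |
| Table 9-1, years 3–4 | Week 176 | 176 − 152 = 24 weeks | 200 − 152 = 48 weeks | 1 (Week 164) becomes 3 (164, 176, 188) |
| SAP amended | Week 128 | 128 − 116 = 12 weeks | 140 − 116 = 24 weeks | 0 becomes 1 (128) |

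In the first two years the tests are mostly 12 weeks apart on both schedules. A test missed at Week 68, for example, gives 80 − 56 = 24 weeks.

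**Step 5: was this still live at the protocol date?** The synopsis puts the start at approximately June 2018. From 01 June 2018 to 22 July 2020 is 782 days, and 782 / 7 = 111.7 weeks. On that start date no subject had reached Week 128, so Weeks 128 and 176 lay ahead of everyone. The early visits may have passed. The parent database lock (05 Nov 2019, section 7.1) is 260 days, or 37.1 weeks, before the protocol date. If every Phase 2 subject had entered by the lock, which is an assumption, Weeks 8, 20 and 32 were behind all of them and 9 − 3 = 6 of the Table 9-1 visits could still arise.

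**The case against.** The strongest reply is that the rule waives nothing. The test stays on the schedule, the Sponsor can refuse any remote visit, and a home dose without the scheduled test would depart from Table 9-1. All of that stands. A reader might infer that the plan intends untested home dosing, and the documents do not support that. What remains is that the rule sets its own conditions and the test is not one of them.

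A reader might also infer that the pregnancy stop is left with no trigger. That goes too far. Any evidence of pregnancy requires IMP to be stopped (9.3.5), a reported pregnancy ends dosing (11.1.1.12), and a test is required after a missed cycle or on suspicion (11.3.2), which may come sooner than the next scheduled one. Women must also abstain or use dual contraception (9.3.2). These safeguards limit the gap without closing it. Contraception does not detect a pregnancy, and the 11.3.1 footnote that places the test at the site is attached to the entry that also covers repeat tests for a missed cycle.

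Footnote i keeps the site for ESR only, which could be read as freeing the dip stick from the site. But 9.1.3.1.2 and 11.3.1 still say site, and footnote i describes no alternative. Section 11.3 refers further detail to the laboratory manual, which is not available here and might describe an off-site test. Even so, nothing in the protocol or SAP would make the result a precondition of the home dose.

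Finally, Table 9-1 itself schedules four doses without a test, so some untested dosing is accepted, and the documents reviewed quantify no fetal hazard. Both points argue for a modest rating.

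**Conclusion.** The gap is real and modest. Under the remote-visit rule, a woman of childbearing potential can be dosed at home without the scheduled pregnancy test at 9 dosing visits on Table 9-1 with the examination weeks of 9.1.3.1.2, or at 13 on the SAP's amended schedule. These are counts of scheduled visits where the situation can arise, not of expected missed tests. The documents do not show how many visits would be remote or how many of the up to 286 subjects are of childbearing potential.

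The 48-week interval should not be quoted as settled. It holds only if Table 9-1 governs and no other test is done in between; on the SAP schedule the corresponding figure is 24 weeks. The conclusion that no off-site method is given does not depend on which schedule applies.

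**What to change.** Add one sentence to the remote-visit paragraph in the synopsis, 9.1.1 and SAP 3.1: for women of childbearing potential, at any visit where the urine pregnancy test is scheduled, a negative dip stick (sensitivity at least 25 mIU/mL, as in 11.3.2), done at home or locally and reported at the remote visit, is required before the home dose. The dip stick should travel by the same route as the home IMP, whatever that is. The protocol does not say how IMP reaches a subject who self-injects, and 10.2.3 describes only a nurse carrying it. Remote visits otherwise stay as they are.

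This is a cheap improvement, since the test is already scheduled and the central laboratory already supplies the materials to sites. The costs are a small supply expense and reliance on a self-reported result where the test is done at home.
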